## 8. GENERAL ANALYSIS CONSIDERATIONS

The statistical analyses will be reported using summary tables, listings, and figures (TLFs). The International Council for Harmonisation of Technical Requirements for Pharmaceuticals for Human Use (ICH) numbering convention will be used for all TLFs.

Unless otherwise noted, all statistical testing will be 2-sided and performed at the 0.05 significance level. Tests will be declared statistically significant if the calculated  $P$ -value is  $\leq 0.05$ .

Continuous variables will be summarized by presenting the number of observations, means, standard deviations (SDs), medians, minimums, and maximums.

Categorical variables will be summarized by presenting counts and percentages of subjects in corresponding categories. All possible categories defined in the CRF will be populated, even with zero counts. Percentages for missing values are omitted and do not account for the percent calculation of other categories. Percentages are based on the total category count, excluding the missing category if not otherwise mentioned. The total number of subjects is used as the denominator in certain tables (e.g., adverse events [AEs]). Footnotes will specify the percent basis in those cases.

Baseline summaries will be presented by treatment sequence and include a total summary column.

Individual subject data obtained from the eCRFs, external vendors, central clinical laboratory, central ECG laboratory, and any derived data will be presented by subject in data listings.

The version of the WHODrug and Medical Dictionary for Regulatory Activities (MedDRA) coding dictionaries used for coding of concomitant medications and medical histories, respectively, will be specified in the final Medical Coding Plan.

After all the data have been verified, coded if necessary, and entered into the database, a review will be performed.

The analyses described in this plan are considered a priori in that they have been defined before breaking the blind.

Any analyses performed after breaking the blind will be considered post hoc and exploratory. Post hoc analyses will be labeled as such on the output and identified in the CSR.

All analyses and tabulations will be performed using SAS® statistical software, version 9.4 or higher (SAS Institute Inc). Tables, listings, and figures will be presented in RTF format.

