Although summaries will be presented for cough frequencies, a log transformation will be used prior to statistical analyses because of the skewed nature of the data. The cough frequency counts will be log transformed prior to calculation of the change from baseline value for each subject. The resulting changes from baseline on the natural log scale will be used as dependant value in statistical testing. All statistical testing will be at the 5% level of significance (2-sided), and 2-sided 95% confidence intervals will accompany all point estimates for the comparison between treatment groups.

A mixed-effect model suitable for the crossover design will be used to compare the two treatment groups' change from baseline in cough frequency on the log scale. The model will include fixed effects for treatment sequence [S1, S2], period [Period 1, Period 2], treatment [ADX-629, placebo] and correlated errors due to treatment. The period-specific baseline values will be included as a covariate.

If there are zero cough frequencies within the data, all values will have 0.1 added to their cough frequency (equating to 1 cough every 10 hours) prior to transforming the data.

The least-squares mean (LSM) change from baseline on the log scale will be presented for each treatment group and the difference between treatment groups.

Estimates from the mixed-effect model will be back-transformed to estimate the ratio comparison to baseline for each treatment group, and the difference between treatment groups will be back-transformed to estimate the ratio comparison to baseline for the ADX-629 group adjusted for placebo. All ratios will be accompanied by the corresponding 95% confidence interval (CI) and p-value.

All model assumptions will be checked by evaluating model residuals. Should the evaluation of residuals indicate a problem with the model assumptions, an alternative analysis will be performed by analyzing the count data on the original scale (observed counts) where the point estimate and confidence interval of the Hodges-Lehmann's median difference for paired groups will be used.

The analysis will also be performed for subgroups based on baseline awake cough frequency median, tercile and quartile classifications as follows:

- Median (< Median/ >= Median)
- Tercile (< Tercile 1/ >= Tercile 1, < Tercile 2/ >= Tercile 2)
- Quartile (< Quartile 1/ >= Quartile 1, < Quartile 2/ >= Quartile 2, < Quartile 3/ >= Quartile 3)

[figure not shown]

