Baseline for the above classifications will be the average of the pre-dose values in period 1 and period 2 for each subject.

The key secondary efficacy analysis of awake cough frequency will be repeated for the PP population.

Additionally, the number and percentage of subjects with  $\geq 30\%$ ,  $\geq 50\%$  and  $\geq 70\%$  reduction from baseline, at Day 14, will also be presented by treatment group.

Subjects will be classified as a responder/non-responder for each category ( $\geq 30\%$ ,  $\geq 50\%$  and  $\geq 70\%$  reduction) and treatment groups will be compared using a generalized estimating equation (GEE) for logistic regression with an exchangeable working correlation structure. The model will include fixed effects for treatment sequence [S1, S2], period [Period 1, Period 2] and treatment [ADX-629, placebo]. The period-specific baseline values will be included as a covariate. The odds ratio between ADX-629 and placebo, 95% confidence intervals for the odds ratio, and P-value for the covariate-adjusted treatment comparison will be presented.

Should the GEE model not converge, the model may be adjusted by removing factors or changing the correlation structure. If the GEE is found to be not appropriate for the data a Fisher's exact test will be used to calculate the odds ratio. The final model will be specified in the footnotes of the appropriate tables.

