### 12.2.3 Global Rating of Change Scores for Cough Severity and Frequency

Subjects will complete the Global Rating of Change on Day 14 of each treatment period.

Subjects will rate the Change in Cough Frequency and Change in Cough Severity on the following scale:

- Worse
- About the Same
- Better

Frequency counts will summarize the Global Rating of Change scores and percentages for cough frequency and cough severity change scores separately for each treatment group. The difference between treatment groups, for the change, will be tested using the Cochran–Mantel–Haenszel (CMH) row mean score difference test. The p-value for the difference will be presented.

In addition to the change, the degree of change (for both cough severity and cough) frequency will also be provided on the following scale:

1. A Very Great Deal Better
2. A Great Deal Better
3. A Good Deal Better
4. Moderately Better
5. Somewhat Better
6. A Little Better
7. Almost the Same; Hardly Any Better at All
8. Almost the Same; Hardly Any Worse at All
9. A Little Worse
10. Somewhat Worse
11. Moderately Worse
12. A Good Deal Worse
13. A Great Deal Worse
14. A Very Great Deal Worse

[figure not shown]
The degree of change will be summarized by frequency counts and percentages for each treatment group.

Global rating of change scale will be remapped and given scores to create a continuous endpoint. A lower score will be considered a more positive outcome. The continuous endpoint will be summarized for each treatment group and appropriate hypothesis testing may be performed as a post-hoc analysis, if justified by the data.

All analyses will be repeated for the median, tercile and quartile group classifications based on the baseline awake cough frequency as described in the Key Secondary Efficacy Analyses Section.

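### Baseline-cough subgroup tests on nine efficacy endpoints may be declared significant at p≤0.05, with no exploratory label and no interaction test

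*SAP*

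**What the plan says.** SAP 8 sets the general rule: "Unless otherwise noted, all statistical testing will be 2-sided and performed at the 0.05 significance level". It continues: "Tests will be declared statistically significant if the calculated" p-value is at or below 0.05. The same section describes the planned analyses as defined before unblinding, and keeps the exploratory label for analyses added afterwards.

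For awake cough frequency, SAP 12.1.1 then adds: "The analysis will also be performed for subgroups based on baseline awake cough frequency median, tercile and quartile classifications as follows". The subgroups (called rows below) are:

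- "Median (< Median/ >= Median": 2 rows.
- "Tercile (< Tercile 1/ >= Tercile 1, < Tercile 2/ >= Tercile 2": 4 rows.
- "Quartile (< Quartile 1/ >= Quartile 1, < Quartile 2/ >= Quartile 2, < Quartile 3/ >= Quartile 3": 6 rows.

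Subjects are classified once: "Baseline for the above classifications will be the average of the pre-dose values in period 1 and period 2 for each subject".

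SAP 12.1.2, 12.2.1 and 12.2.2 apply the same rows to 24-hour cough frequency, VAS, LCQ total and CQLQ total. SAP 12.2.3 does so for the two global ratings of change ("All analyses will be repeated for the median, tercile and quartile group classifications based on the baseline awake cough frequency"), and SAP 12.2.4 for PGIC and CGIC. The first five endpoints use the crossover mixed model; the last four use a CMH row mean score test.

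The mixed model contains sequence, period, treatment and period-specific baseline. It has no treatment-by-baseline term. Neither document gives a hierarchy, an adjustment or a nominal label for the rows. The softer, optional wording in SAP 12.1.3 covers a different set of subgroups.

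**The concern.** Read together, SAP 8 and 12.1.1 allow a p-value of 0.05 or less in any row of any of the nine endpoints to be reported as statistically significant. The rows are small and overlapping, and they are tested many times over. The risk is greatest when an endpoint shows nothing overall and one row does, because that is when a subgroup finding is most likely to be carried into the next trial's entry criteria.

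The rows also cannot show whether the effect depends on baseline cough rate. A small p-value on one side of a cut and a large one on the other is not evidence of a difference between the two sides. That needs a direct test of the difference, and none is planned.

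**Working it through.** **Inputs.** Level: two-sided 0.05 (SAP 8, repeated in 12.1.1). Sample size: about 50 randomised (SAP 5). The number analysed is not given, so 36 to 50 is assumed. The plan states no error rate for the subgroups, so there is no figure of its own to reproduce. The power statement in SAP 5 cannot be checked because its standard deviation is not in the public copy; nothing below depends on it.

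**Step 1: count.** Listed rows: 2 + 4 + 6 = 12. Quartile 2 is the median, so 12 − 2 = 10 are distinct. Over nine endpoints that is 9 × 10 = 90 distinct tests. If every test had exact 5% size, 90 × 0.05 = 4.5 would be expected at p≤0.05 with no treatment effect.

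**Step 2: upper reference.** If the rows were independent, the chance of at least one false positive per endpoint would be 1 − 0.95^10 = 40.1%. They are nested or complementary sets of the same subjects, so the true figure is lower and has to be simulated.

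**Step 3: simulation for a modelled endpoint.** There were 40,000 trials per sample size. Within-subject treatment differences were normal and unrelated to baseline, with half the subjects in each sequence. Each row was tested with the period-adjusted crossover t statistic, t = (m1 − m2) / √[s²(1/n1 + 1/n2)] on n1 + n2 − 2 degrees of freedom. Here m1 and m2 are the sequence means of the within-subject difference between periods. The period-baseline covariate was left out.

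| Subjects analysed | Any row p≤0.05 | Any row favouring ADX-629 | Any row, given overall test not significant |
|---|---|---|---|
| 36 | 24.4% | 12.7% | 20.6% |
| 40 | 23.9% | 12.5% | 20.2% |
| 44 | 24.0% | 12.4% | 20.2% |
| 48 | 23.7% | 12.2% | 19.9% |
| 50 | 24.1% | 12.5% | 20.3% |

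The Monte Carlo standard error of the first column is √(0.24 × 0.76 / 40,000) = 0.2 percentage points, so the figure barely depends on sample size. At 50 subjects the median cuts alone give 9.8%, the tercile cuts 15.6% and the quartile cuts 20.0%.

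**Step 4: CMH endpoints.** A simulated 7-point scale with 48 subjects and two ratings each gives 22–23% for any row if the test is stratified by subject. If it is unstratified, the rate is 23%, 11% or 5% at assumed within-subject correlations of 0, 0.3 or 0.5. This matches PGIC and CGIC. The global ratings are tested on three categories, so for them it is only a guide.

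**Step 5: all nine endpoints.** Treating all nine as paired t tests with 48 subjects, the chance of at least one false row anywhere is 91% if the endpoints are independent, 80% at an assumed correlation of 0.5 and 49% at 0.9.

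**Step 6: precision.** The 95% CI half-width for a mean paired difference is t(0.975, n−1)/√n standard deviations: 0.284 at n = 50 and 0.635 at n = 12, about the size of an outer quartile. The ratio is 0.635 / 0.284 = 2.2.

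**The case against.** The strongest reply is about context. This is a Phase 2 trial whose primary objective is safety. Every efficacy endpoint is secondary, and formal hypotheses are written only for awake cough frequency. No primary-endpoint error rate is touched. Neither document states an aim to show effect modification, and a small p-value in a table is not yet a claim. SAP 8 also says 'unless otherwise noted', which leaves room for an exemption.

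Most of that stands as a limit on severity. It does not remove the point: no exemption is written, the planned analyses are set apart from exploratory ones, and the stated rule attaches the word significant to these rows.

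A second reply is also right. The 24% counts results in either direction and was derived for paired-difference tests, so it is not established for the four CMH endpoints. Those endpoints also have no regression model to which an interaction term could be added.

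A reader might go further and argue that significance should be restricted to a single test across the whole plan, citing 16 whole-population tests (nine endpoints, six responder cuts and LDL-C) and 1 − 0.95^16 = 56%. That figure assumes independence. The two cough frequencies come from the same recording, the responder cuts are nested, and LDL-C sits under safety. In a trial of this kind the wider restriction is debatable, and the subgroup point does not need it.

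**Conclusion.** The concern holds for the baseline-cough subgroups. For each of the five modelled endpoints, the rule as written carries about a 24% chance of at least one falsely significant row at 40 to 50 subjects. About 12% is the chance of one favouring ADX-629. When the overall result is null, about a 20% chance of a significant row remains. These figures assume no treatment effect and normal differences unrelated to baseline.

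Three stronger readings are tempting but not supported. First, the 24% cannot be applied to all nine endpoints, because the SAP does not say how the CMH test handles pairing. Second, multiplying all 108 listed tests by 0.05 to get 5.4 false positives counts the Quartile 2 rows twice; 4.5 is the figure for distinct tests, and even that assumes exact 5% size throughout. Third, a false row somewhere in the trial cannot be called very likely without an assumed correlation between endpoints, since the range is 49% to 91%.

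The change should be made, but the plan's primary conclusions do not depend on it.

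**What to change.** 1. In SAP 8 and 12.1.1, state that the median, tercile and quartile subgroup results are exploratory and that their p-values are nominal and will not be declared statistically significant.
2. Drop the two Quartile 2 rows.
3. For awake and 24-hour cough frequency, VAS, LCQ total and CQLQ total, add one interaction of treatment with continuous log baseline awake cough frequency, together with its main effect. The main effect is needed because the planned covariate is the period-specific baseline; for VAS, LCQ and CQLQ, awake cough frequency is not in the model at all. Use the SAP's own subject-level classifier (the average of the two pre-dose values), or state and justify a change to the study baseline of SAP 8.1. Base any statement about effect modification on this test.
4. For the global ratings of change, PGIC and CGIC, show the subgroup results descriptively.

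**Cost.** No new data are needed: only SAP wording and two terms in five models. Subgroup p-values can no longer be called significant. The interaction test assumes linearity on the log scale and has limited power. As a guide, with difference SD σ, the contrast between two halves of 25 has standard error σ√(2/25), twice the overall σ/√50. A clear difference in effect could therefore still be missed at about 50 subjects.

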#### Additional Secondary Endpoints:

- Percentage of subjects with  $\geq 30\%$ ,  $\geq 50\%$ , and  $\geq 70\%$  reduction from baseline in Awake Cough Frequency to Day 14 of Treatment Period
- Percentage of Subjects with  $\geq 30\%$ ,  $\geq 50\%$ , and  $\geq 70\%$  reduction from baseline in 24-hour Cough Frequency to Day 14 of Treatment Period
- The number and percentage of subjects with a  $\geq 30\text{mm}$  reduction from baseline to Day 14 of Treatment Period
- The number and percentage of subjects with a  $\geq 1.3$  point increase from baseline to Day 14 of Treatment Period

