## 4. STUDY DESIGN

ADX-629-CC-001 is a Phase 2, multicenter, randomized, double-blind, placebo-controlled, two-period crossover trial to evaluate the safety, tolerability, and efficacy of ADX-629 300 mg administered orally BID for 14 days to approximately 50 adult subjects with refractory or unexplained chronic cough.

Subjects will be screened over a period of up to 3 weeks. Eligible subjects will be randomized to one of two treatment sequences. Subjects in one sequence will receive ADX-629 in Treatment Period 1 and matching-placebo in Treatment Period 2, while subjects in the other sequence will receive the matching placebo in Treatment Period 1 and ADX-629 in Treatment Period 2.

[figure not shown]
Subjects will receive their allocated treatment for 2 weeks within each treatment period. Each subject will have a washout period of 2 weeks  $\pm$  2 days between the two trial periods and will undergo a follow-up assessment approximately 1 to 2 weeks after the last dose of trial treatment. Subjects will be required to attend visits for screening and at the start and end of each treatment period. Each visit will require the subject to attend the clinic or to be visited by research staff on consecutive days. At Screening (Visit 1) and on Days 0 (Visit 2 and Visit 6) and 13 (Visit 4 and Visit 8) of each treatment period, the subject will be fitted with a cough recorder to collect cough count data over a period of 24 hours. The cough recorder will be removed the next day once the 24-hour recording has been completed. The trial will include 5 cough recorder sessions in total.

The trial duration for each subject will be up to 11 weeks as follows: up to 3 weeks for screening, 2 weeks for each treatment period, a 2-week washout between treatment periods, and a 2-week follow-up period.

Should a subject discontinue trial treatment, they will be requested to participate in an early (ET) termination visit as soon as possible after the subject stops taking trial treatment. The subjects should have their follow-up visit 1 to 2 weeks after their last dose of trial treatment; however, if their ET visit is more than 1 week after their last dose, they will not be required to have a follow-up safety assessment.

The follow-up safety assessment will be conducted as an in-clinic visit for follow-up laboratory parameters, vital signs, or electrocardiogram (ECG) parameters.

The trial design is illustrated in Figure 1.

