## 5. DETERMINATION OF SAMPLE SIZE

The power is increased to over 90% for treatment improvements greater than 35%. By allowing for a reduction in power due to subject withdrawals, approximately 50 subjects will be randomized.

The null ( $H_0$ ) and alternative ( $H_1$ ) hypotheses for the key secondary efficacy endpoint (awake cough frequency) can be expressed as:

$$H_0: \mu_{ADX} = \mu_{PLA}$$

$$H_1: \mu_{ADX} \neq \mu_{PLA}$$

where  $\mu_{ADX}$  and  $\mu_{PLA}$  are the mean changes from baseline in cough frequency for ADX-629 and placebo respectively.

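### The cough-frequency responder GEE saturates the four sequence-by-period cells, and its non-convergence trigger does not reliably catch an empty cell, chiefly at the ≥70% cut-off

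*SAP*

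**What the plan says.** SAP 12.1.1 classifies each subject in each period as responder or non-responder at three cut-offs. It compares treatments by logistic GEE with an exchangeable working correlation. "The model will include fixed effects for treatment sequence [S1, S2], period [Period 1, Period 2] and treatment [ADX-629, placebo"], and the period-specific baseline is added as a covariate. SAP 12.1.2 applies the same methods to 24-hour frequency.

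Two safeguards follow. First: "Should the GEE model not converge, the model may be adjusted by removing factors or changing the correlation structure". Second, if the GEE proves unsuitable for the data, Fisher's "exact test will be used to calculate the odds ratio". No criterion for unsuitability is given, no order of factor removal is set, and nothing covers empty cells. The final model is to be footnoted in the tables.

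The responder rates are listed in SAP 3.4 under Additional Secondary Endpoints, as the percentage of subjects reaching each "reduction from baseline in Awake Cough Frequency to Day 14 of Treatment Period", with a matching entry for 24-hour frequency. The protocol's endpoint list does not contain them. Under SAP 8, "all statistical testing will be 2-sided and performed at the 0.05 significance level". SAP 5 says that "approximately 50 subjects will be randomized", and SAP 8.2 rules out imputation.

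**The concern.** In a two-sequence, two-period crossover, treatment is the sequence-by-period interaction. An intercept plus sequence, period and treatment is therefore four parameters for four cells. With at most about 25 subjects per cell and a strict cut-off, a cell may hold no responder at all. The data are then separated and the treatment log odds ratio is not identified in any useful sense.

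Non-convergence is the SAP's only objective signal of trouble. If the fit stops at a large finite value instead, the table shows an enormous odds ratio with a small robust p-value, and SAP 8 calls it significant. If the analyst does notice, the remedy is chosen after seeing the fit, and the final fallback ignores that each subject contributes two responses.

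**Working it through.** **Inputs.** About 50 randomized (SAP 5), two sequences (SAP 4), observed data only (SAP 8.2), two-sided 0.05 (SAP 8). Assumed, because the documents do not give them: 1:1 allocation, responder rates, withdrawals leaving 45 completers (22 and 23 per sequence), and the within-subject correlation.

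**1. The plan's own figure.** SAP 5 gives power only for awake cough frequency: over 90% for improvements above 35%. The SD is not visible, so this cannot be reproduced. Solving backwards at exactly 90% and 35%, SD of the between-treatment log difference = |ln 0.65| × √n / (1.960 + 1.282) = 0.94 (n=50), 0.89 (n=45) or 0.84 (n=40). No figure is given for the responder analysis.

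**2. Saturation.** S1 takes ADX-629 first. Leaving the baseline covariate aside, logit(S1P1) − logit(S1P2) is treatment minus period, and logit(S2P2) − logit(S2P1) is treatment plus period. Hence

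log OR = ½ [(S1P1 − S1P2) + (S2P2 − S2P1)], in logits.

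One empty cell sends a logit to minus infinity and the log OR with it.

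**3. Chance of an empty cell.** Treating cells as independent, P = 1 − [1 − (1−p)^22]² [1 − (1−p)^23]².

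| Rate p | (1−p)^22 | (1−p)^23 | P(at least one empty cell) |
|---|---|---|---|
| 4% | 0.407 | 0.391 | 87% |
| 8% | 0.160 | 0.147 | 49% |
| 15% | 0.028 | 0.024 | 10% |
| 25% | 0.0018 | 0.0013 | 0.6% |

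Simulation with latent correlation 0.5 gave 85%, 47% and 10% for the first three rows.

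**4. Which cut-offs.** As illustration, take normal log changes, no treatment effect, and the SD range 0.84–0.94 from step 1. With uncorrelated periods and zero mean change, the SD of one period's change is 0.84/√2 = 0.59 to 0.94/√2 = 0.66, and the response rate is Φ(ln(1−r)/SD):

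- ≥30%: rate 27–30%, P(empty) under 0.5%
- ≥50%: rate 12–15%, P(empty) 20–10%
- ≥70%: rate 2–4%, P(empty) 98–91%

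With correlation 0.5 between the two changes and a 20% mean placebo reduction, the ≥70% rate is 12–15% and P(empty) 20–10%. So the range is roughly 10–98% at ≥70%, 0–20% at ≥50%, and negligible at ≥30%.

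**5. Does the trigger catch it?** Example with 25 per cell: S1P1 4, S1P2 0, S2P1 3, S2P2 2 responders, so ADX-629 6/50 and placebo 3/50. Hand-written GEE code for the planned model reported convergence under three different stopping rules at log OR 3.96 (OR about 52), robust SE 0.54, p<0.0001. Fisher's test on the same counts gives OR 2.1, p=0.49. The GEE without sequence gives log OR 0.71, p=0.35.

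Null simulations:

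- statsmodels, 22/23 per sequence, 400 trials at a 4% rate: 157 of 327 empty-cell trials reported convergence, 47 of them with p≤0.05. Overall rejection was about 12% at 4%, 5% at 8% and 4% at 15%. A separate 600-trial run gave 72/600 = 12% at 4% and 30/600 = 5% at 8%.
- Hand-written code, 25 per sequence, latent correlation 0.4, 1500 trials per rate, range over stopping rules: 19–35% at 5%, 13–15% at 10%, about 6% at 15%, and 6.3% at 30%, where no cell was empty.

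**6. The remedies on offer.**

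- *Changing the correlation structure.* Under independence the estimate simply diverges, the log OR growing by 0.5 per iteration. Separation is not cured.
- *Removing factors.* Dropping sequence leaves three cell parameters, and with exactly one empty cell the fit converged in 98–100% of trials. Hand-written code rejected the null in 3.0% of all trials at a 5% rate and 4.9% at 10%, but in 13% (10% rate) and 21% (15% rate) of trials with exactly one empty cell. A statsmodels run rejected in 126/600 = 21% at a 4% rate.
- *Fisher's test.* Null rejection was at most 1.5%. Power in empty-cell trials at correlation 0.5, Fisher against exact McNemar: 33% v 39% (response 15% v 4%), 43% v 48% (20% v 8%), 81% v 86% (30% v 10%). At correlation 0.25 the gap was 1–2 points; at zero, Fisher was equal or slightly better.

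Hand check with 45 completers, 8 v 2 responders: Fisher p=0.090. Exact McNemar gives 2 × 0.5⁶ = 0.031 if both placebo responders also responded on ADX-629 (6 discordant v 0), and 2 × 56/1024 = 0.109 if neither did (8 v 2).

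**The case against.** Much of the opposing case stands. These endpoints are Additional Secondary, the primary objective is safety, and the key secondary analysis is a separate mixed model on log change. The trigger is leaky rather than useless: in the 600-trial statsmodels run, non-convergence flagged 180 of 280 empty-cell trials at an 8% rate and 240 of 506 at 4%. The unsuitability clause could be read to cover an empty cell, and the footnote makes the final model visible.

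A reader might infer more than the documents support:

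- *That the model has four fixed effects and the odds ratio is always infinite.* The SAP names three; the fourth parameter is the intercept. With exchangeable correlation and the baseline covariate, the fit may stop at a finite, meaningless value. That makes non-convergence a poorer trigger.
- *That the error rate is badly inflated at every cut-off.* Among fits that reported convergence, rejection at a 4% rate was 24% (71/295), but that is conditional. Over all trials statsmodels gave about 12%, and near nominal at 8% and above. At ≥30% the problem is negligible.
- *That Fisher's test creates false significance, or loses much power here.* It is conservative, and its loss in the trials where it would be used is modest.
- *That the only outcomes are false significance or lost pairing.* Factor removal keeps the pairing. Its weakness is that it is optional, unordered and chosen after the fit, and does not reliably hold the error rate when a cell is empty.

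**Conclusion.** The rule is wrong as written and should be fixed. An empty sequence-by-period cell leaves no meaningful treatment odds ratio, and non-convergence does not reliably detect it. Two implementations agree that an empty-cell fit can pass as converged with p≤0.05. They disagree on how often: about 12% overall at a 4% rate in statsmodels, against 19–35% at 5% and 13–15% at 10% in hand-written code. The two used different sample sizes and correlations, statsmodels standard errors were numerically unstable under separation, and SAS, which the SAP specifies, was not run. The size is therefore software-dependent.

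The empty-cell probabilities do not depend on software, but they rest on assumed responder rates and 22–25 subjects per cell. They point mainly to the ≥70% cut-off, possibly ≥50%, and not ≥30%. The Fisher fallback is a lesser fault: an unpaired test in a crossover, with an undefined trigger, costing about 5–6 points of power at within-subject correlation 0.5 and less at lower correlation. The key secondary conclusion is not at risk.

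**What to change.** In SAP 12.1.1, and through it 12.1.2:

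1. State that if any of the four sequence-by-period cells has no responder or no non-responder, the GEE is not used for that cut-off.
2. In that case report the counts, the paired difference in responder proportions with its 95% CI, and one pre-specified exact paired test in place of Fisher's exact test: exact McNemar, or the Mainland-Gart test if period adjustment is wanted. In null simulations at 5% and 10% response rates, both rejected in at most 1.8% of trials.
3. Delete the open permission to remove factors or change the correlation structure, or replace it with this fixed rule.

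The cost is SAP wording and one extra procedure call. The downside is small: subjects with only one period do not enter the paired test, and exact McNemar is not period-adjusted, though neither is Fisher's test.
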